- 5.6 *Sample receipt/chain of custody/Accountability*
- 5.7 *Tissue Sample Transfer*

6. Assessment of Safety

- 6.1 *Ethics Reporting*

8. Direct Access to Source Data and Documents

9. Ethics & Regulatory Approvals

10. Data Handling

- 10.1 *Case Report From*
- 10.2 *Record retention and Archiving*
- 10.3 *Compliance*
- 10.4 *Clinical Governance issues*
- 10.4 *Non Compliance*

11. Finance & Publication Policy

Study Synopsis

Title	Role of the oral microbiome & mucosal immunity in COVID-19 disease: diagnostic/prognostic utility in South Asian populations
Protocol Short Title/Acronym	Oral Microbiome & Mucosal Immunity in COVID-19 disease (MIMSA)
Protocol Version number and Date	Version 2.0 02/05/2023
Study Phase if not mentioned in title	1
Is the study a Pilot?	No
Study Hypothesis	That differences in morbidity and mortality of South Asian populations following COVID-19 disease are related to differences in mucosal immunity and the oral microbiome.
Study Duration	18 months duration
Methodology	
Cross sectional with longitudinal component
 
 • South Asian (SA) and White British (WB) populations • Blood and stimulated whole mouth fluid (SWMF) • Uninfected subjects, and COVID-19 patients in both populations. • Medical History, Oral disease questionnaire and clinical examination • Separation of SWMF into pellet for DNA extraction for microbiomics and supernatant for cell phenotype analysis, cytokines and antibodies to SARS-CoV2 antigens
Sponsor name	King's College London/GSTT
Chief Investigator	[name]
REC number	22/SC/0105
Medical condition or disease under investigation	COVID-19 disease
Purpose of clinical trial	To collect clinical samples from defined patient groups for laboratory analysis
Primary objective	Determining whether in the mouth there are differences between the participant groups in the nature and activity of mucosal innate immunity, in immune responses to SARS-COV2 antigens, or in the oral microbiome
Secondary objective (s)	1. To determine whether differences in mucosal immunity or differences in the oral microbiome correlate with susceptibility to COVID-19

	infection, or to disease severity or indicate speed or efficacy of disease control. 2. Determining whether the presence of pre-existing oral disease is related to susceptibility to SARS-CoV2 infection, to severity of COVID-19 disease or relates to the nature of mucosal immunity and to the composition and activity of the oral microbiome
Number of Subjects/Patients	Up to 800 subjects will be recruited, comprising up to 400 SA and 400 WB, each including patients, recovered and uninfected subjects.
Trial Design	Cross sectional with longitudinal component. Samples of SWMF, and blood and a detailed mouth examination on all participants. Lymphocyte phenotypes in blood and SWMF compared, cytokines and serum and secretory antibodies to SARS-CoV2 antigens. DNA extraction from SWMF for meta-analysis of oral microbiome, and metabolome and proteome analysis
Endpoints	
 1. Patients recruited 2. Samples collected and processed 3. Generation of raw data
Main Inclusion Criteria	
 • South Asian* and White British persons and those diagnosed with current or past symptomatic or asymptomatic SARS-CoV2 infection, or uninfected. • Aged 18 or over. • Able to understand and consent. • For in patient groups: Confirmed COVID-19 positivity, symptoms and symptom onset within the past 21 days;
Statistical Methodology and Analysis	
A total sample size of up to 800 participants, up to 400 of which will provide samples at three further time points. Between 30 and 50 values per parameter would be needed to demonstrate statistical differences on a cross sectional basis and 30-40 per parameter on a sequential basis.
 
The microbiome, clinical data and immunome data will be associated using Spearman correlations. A Mann–Whitney U-test will be used to determine the median differences of continuous clinical variables. For more than two groups, the Kruskal–Wallis test with post-hoc Dunn test will be used.

*South Asian defined as those of Indian sub-continent origin.

There is no device or product used in this study

Glossary of Terms and Abbreviations

AE Adverse Event

AR	Adverse Reaction
ASR	Annual Safety Report
CA	Competent Authority
CI	Chief Investigator
CRF	Case Report Form
CRO	Contract Research Organisation
DMC	Data Monitoring Committee
EC	European Commission
GAfREC	Governance Arrangements for NHS Research Ethics Committees
GSTT	Guys & St Thomas Hospital
ICF	Informed Consent Form
ISRCTN	International Standard Randomised Controlled Trial Number
KCH	King's College Hospital
KCL	King's College London
MA	Marketing Authorisation
MS	Member State
Main REC	Main Research Ethics Committee
NHS R&D	National Health Service Research & Development
PI	Principal Investigator
QA	Quality Assurance
QC	Quality Control
Participant	An individual who takes part in a clinical trial
RCT	Randomised Controlled Trial
REC	Research Ethics Committee
SAE	Serious Adverse Event
SDV	Source Document Verification
SOP	Standard Operating Procedure
SSA	Site Specific Assessment
SWMF	Stimulated Whole Mouth Fluid
TMG	Trial Management Group
TSC	Trial Steering Committee

1. Introduction

Background

SARS-CoV2 primarily infects respiratory mucosae, yet mucosal immunity has barely been studied. There is increasing evidence of the importance of both natural immunity (innate) and of immune responses (adaptive) of mucosal surfaces of the whole of the upper aerodigestive tract and of the lower respiratory tract in protection against disease, but very little is known in relation to COVID. Minor salivary glands appear to be a major site of SARS coronavirus replication (Liu et al 2011) and in the virological phase (first week) extremely high viral loads can be found in saliva (To et al 2020) and may be higher than in the nasopharynx (Yoon et al 2020): The oral cavity is rich in ACE2 receptors (Xu et al 2020; Huang et al 2020) especially in the epithelial cells of the many hundreds of minor salivary glands (Wu et al 2020). SARS-CoV2 can also be found in gingival crevicular fluid. It is known that in viral diseases T-cells and cytokines are altered in both systemic and mucosal immunity but have not been much explored in the mucosal response of the upper aero-digestive tract.

The role of oral mucosal immunity has been well elucidated in a number of oral and systemic diseases (Feller et al., 2013; van Splunter et al., 2018; Naiff et al., 2014). The host immune response elicited by SARS-CoV2 upon dysregulation leads to high morbidity and mortality. Thus, the role of mucosal immunity in the pathogenesis of COVID-19 is of paramount importance. Although a number of host immune factors including cytokines (notably IL-6, IL-1 β , IFN- γ) and T cell phenotypes (Th1, Th2, Th-17, Tregs, Tfh cells) have been implicated in a few reports to play important roles in systemic immunity to SARS (Chen and Wherry, 2020; McElvaney et al., 2020), their role in mucosal immunity remains largely unexplored.

Dysregulated immune responses have been shown to orchestrate disease pathogenesis in many viral infections including dengue and HIV (Uno and Ross, 2018; Wang et al., 2016). Decrease in Tregs, Tfh cells and germinal centre formations have been shown in lung autopsies of severe COVID-19 patients (Duan et al 2020). Although class switching from IgM to IgG antibodies takes about 7 days in most infections, specific anti-SARS-CoV2 IgM and IgG responses have been detected within 2-3 days (Thevarajan et al., 2020; Suhandynata et al., 2020). These findings implicate B cell responses as being differentially orchestrated by the T cells. Taken together, these data indicate that COVID-19 is a disease driven via host immune system so that understanding the immune players and the molecular pathways involved is of utmost importance for rational patient management.

Recent years have seen great increases in our understanding of the oral microbiome in health and disease and its relationship to gut, lung and nasal microbiomes. All mucosal surfaces have a normal stable microbial flora (the microbiome) which protects against invasion by pathogens. However, in COVID any role of a mucosal microbiome is completely unknown. Oral diseases, especially periodontal diseases, allow bacteria and viruses to readily enter the blood stream. It is unclear whether this plays a role in systemic manifestations of COVID. Microbial dysbiosis appears to be a factor in COVID-19 severity. Metagenomic analyses of patients infected with SARS-CoV2 have frequently reported high reads of cariogenic and periodontopathic bacteria,

endorsing the notion of a connection between the oral microbiome and COVID-19 complications (Chakraborty 2020). There is considerable evidence that periodontopathic bacteria are involved in the pathogenesis of several respiratory diseases, and are associated with chronic inflammatory systemic diseases including type 2 diabetes, hypertension, and cardiovascular disease (Patel and Sampson 2020). Advances in high-throughput sequencing have revolutionised our understanding of human-microbe interactions and have led to a substantial rise in knowledge of the human microbiome. With this increased understanding has come an awareness of the significant role that the microbiome of mucosal surfaces plays in several diseases.

Notably, recent studies support the hypothesis that the oral microbiota is of relevance in both acute and chronic lung disease, with poor oral health associated with an increased risk of respiratory disease (Mammen et al 1999). A question is, therefore, whether inflammation in the oral cavity may predispose to SARS-CoV2 infection (Sampson et al 2020). We know that improving oral health results in a reduction in respiratory infections in ICU and nursing home patients (Azarpazhooh et al 2006). Of particular relevance to the current COVID-19 pandemic, risk factors including coughing, hyperventilation and mechanical ventilation have been shown to provide a pathway for members of the oral microbiota to penetrate the lower respiratory tract and cause disease (Bao et al 2020). Co-infections have been significant causes of mortality in many previous viral pneumonia pandemics, including the recent 2009 swine flu outbreak (MacIntyre, et al 2018), and these phenomena appear to be repeating for the current COVID-19 pandemic. Early metatranscriptome analyses indicate the presence of elevated levels of oral commensal bacteria in the bronchoalveolar lavage of COVID-19 patients (Shen et al 2020).

There is increasing evidence of disparities in susceptibility to SARS-CoV-2 infection and subsequent morbidity and mortality amongst groups of different ethnic origin. In the UK, South Asian populations have been identified as a particularly susceptible group, with a high percentage mortality in contrast to similar populations in India, even after taking into account the effect of socio-economic level and of co-morbidities. The extent to which social, environmental and biological factors differ in the two populations and contribute to differences in outcomes from COVID-19 is not known.

Our research will compare the oral microbiome, salivary innate and specific mucosal antibody responses and oral disease among SARS-CoV2-positive patients and controls in the UK and determine their diagnostic and prognostic utility. We will compare mucosal and systemic immunity in order to reveal biomarkers for risk of disease progression so as to enable early initiation of treatment.

The study is part of a UK-India partnership and at the end of the research, data from the UK will be compared with that derived from a similar study with our collaborators in India.

References

Figure: Model of possible interrelationships between innate cellular immunity, cytokines and mucosal antibody in patients with asymptomatic, mild or severe COVID-19 disease. Oral mucosal immunity influenced by host immune dysregulation, underlying oral disease and/or oral dysbiosis determines the level of disease severity in COVID-19. When an individual gets infected with SARS-CoV2, there will be an immediate peak in viral proteins due to the initial proliferation of the virus (virological phase), which lasts about 5-7 days. This antigen peak is shown as a blue line in all the three groups. When the individual's cytokines and T cell responses are modulated appropriately the virus is cleared with no clinical symptoms (asymptomatic) or with very minimal symptoms (symptomatic-mild). The cytokines and T cell responses (green line on the graphs) are short-lived in these two groups. On the other hand, when there is immune dysregulation, underlying oral disease and/or dysbiosis, the cytokines and T cell responses remain upregulated for a long period (cytokine storm) thereby causing tissue destruction (symptomatic-severe), which in turn increases the morbidity and mortality (immunological phase). The protective/virus neutralizing antibodies (red line on the graphs) potentially appear after one week and remain high in the asymptomatic and symptomatic-mild groups of patients. However, in the symptomatic-severe group, the anti-SARS-CoV2 antibodies potentially remain lower and hence might not confer any protection. The graphs depict the expected outcome in the whole mouth fluid. These markers are expected to persist even longer in the peripheral circulation. The proposed study is designed to address these key points and potentially unveil the host immune players that drive the disease pathogenesis in COVID-19.

2 Trial Objectives, Design and Statistics

2.1. Trial Objectives

- Primary Objective

The key aim of this research in South Asian populations and White British populations, is to find out whether differences in COVID-19 morbidity and mortality in similar populations in the UK might be related to mucosal immunity expressed in the mouth and to the oral microbiome (the total bacteria, fungi and viruses living in the mouth). This will be achieved by determining

whether in the mouth there are differences between the participant groups of mucosal natural immunity (innate immunity), immune responses to SARS-COV2 antigens (adaptive immunity), or the oral microbiome

- Secondary Objectives

1. To determine whether differences in mucosal immunity or differences in the oral microbiome correlate with susceptibility to COVID-19 infection, or to progression and recovery from the disease.

2. To determine whether the presence of pre-existing oral disease is related to susceptibility to SARS-CoV2 infection, to severity of COVID-19 disease or relates to the nature of mucosal immunity and to the composition and activity of the oral microbiome

- Primary End Point

- Collection, processing and analysis of samples. Statistically significant quantitative differences in measured mucosal innate immune factors, mucosal adaptive immune factors and/or in the oral microbiome in relation to 1) a comparison between South Asian and White British populations in the UK 2) the degree of severity of COVID in South Asian and White British participants in the UK

- Secondary End point

- Generation of raw data.
- *a comparison between South Asian populations in the UK and in Chennai, India.

**Note: This is the UK part of an international research collaboration between the UK (funded by the MRC) and India (funded by the DBT) with research being carried out separately but in parallel in the two Countries and generating results which will be directly compared.*

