Asymptomatic/mild subjects will be recruited from those identified as positive for SARS-CoV2 carriage in routine testing at KCL or GSTT. In both cases local staff will inform them about the trial and give out a patient information sheet. A medical history will be taken from those who consent to take part in the research

Symptomatic moderate/severe patients will be recruited within Guys and St Thomas Hospital, mainly in conjunction with the GSTT COVID infection teams. Patients will be recruited from those admitted or planned to be admitted to GSTT with a recent onset (≤ 21 days) of symptoms of COVID-19 and a confirmed positive nasal/nasopharyngeal PCR test for SARS-CoV-2. They will be identified and approached by the clinical staff caring for them on the wards who will discuss the trial in outline and offer the PIL. Should the patient wish to consider participation after reading the PIL, the clinical research dentist (summoned by clinical ward staff) will obtain signatures of consent.

Recovered participants will be patients who have had COVID and fulfil the inclusion criteria. They will have either been discharged from GSTT or be attending either the post-COVID or ICU follow-up outpatient clinics and will be sent letters of invitation to participate. They will also be recruited from participating GP PIC sites, KCL sites and GSTT sites

Number of subjects	Subject selection
Group 1. SA1, BW1 Uninfected Subjects (n=100 each)	Uninfected subjects, both South Asian and White British will be recruited by advertisement within KCL or social media, from non-COVID in-patients or outpatients or attending A&E at GSTT and at SARS-CoV2 antigen testing centres and vaccination centres and at PIC sites. They will be furnished with the participant information leaflet and invited to take part in the study. After obtaining informed consent, oral examination, oral & general health questionnaires and samples of blood and stimulated whole mouth fluid (SWMF) (see below) will be taken either on the wards (inpatients), A&E or at the department of Oral Medicine at Guys Hospital
Group SA1v, BW1v (n=50)	In a subset of uninfected subjects from those attending for vaccination or volunteers, blood and SWMF will be taken 2 weeks after the first vaccination and 2 weeks after the second vaccination for immunology and microbiome analysis.

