3.1 Inclusion Criteria

Inclusion criteria
	
 • South Asian and White British persons and those diagnosed with symptomatic or asymptomatic COVID-19 infection, or recovered from COVID infection or previously uninfected. • Aged 18 or over. Able to understand and consent. • For inpatient groups: Confirmed COVID-19 positivity, symptoms and symptom onset within the past 21 days; Be recently (within 7 days) hospitalised with COVID-19 disease; Have COVID-19 disease proven by PCR testing for SARS-CoV-2 within the last 21 days; • Uninfected subjects: no history of COVID-19; not vaccinated; (negative for anti-SARS-CoV2 nucleoprotein antibodies at lab)
---------------------------	--

	
 • Recovered groups: Have had COVID-19 disease proven by PCR testing for SARS-CoV-2. • Those willing to participate on a single occasion but unwilling to participate with longitudinal samples will not be excluded. • Smoking, obesity, diabetes, heart disease, antibiotics or treatment related to COVID is not excluded.
--	--

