We wish to record the severity and extent of active inflammation of the periodontium: a situation where, cumulatively around the mouth, very large areas of eroded or ulcerated gingival sulcular and pocket epithelium may be present. The standard in the field is “PSR/BPE” – periodontal screening and recording/basic periodontal examination. We will record the deepest pocket on every standing tooth as an accurate cumulative measure of inflamed surface area using disposable, appropriately marked, WHO probes. PSR simplifies this to a single code per sextant.

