Relevant Medical history including current medication

Relevant Dental History

Mouth Examination (this will include any previous dental habits)

"PSR/BPE" – periodontal screening and recording/basic periodontal examination.

Adverse Events,

The CRF will also have a withdrawal from study form which will record participants reason for withdrawal when/if known.

Patient Metadata and tissue collection form

Sample ID

Date of collection

Time of collection

Initials of clinician undertaking

Patient Metadata

Age of patient

Sex M/F

Oral Hygiene Habits

Does Patient use toothpaste yes/ no

Patient regularly sees dentist yes/no

History of previous periodontitis yes /no
 If yes to give further details
 If patient is a smoker (standard cigarettes) yes/ no
 Patient smokes e-cigarettes yes/ no

Sample collection

SWMF: stimulated whole mouth fluid sample yes/no
 Volume of SWMF collected (to be detailed at laboratory)
 Blood samples yes/no

The CRF will be updated at all 3 study visits.

The CRF will be completed by the primary investigator at all study visits as well as any named staff working on the trial. All participants will be added to an enrolment log.

Record Retention and Archiving

Source documents containing or relating to clinical data will be kept for five (5) years after termination of the study. The Principal Investigator will maintain study documentation for all participants entered into the study in a secured, locked and alarmed room, ensuring the confidentiality of the information collected. Securing records includes placing written forms in locked file cabinets and/or sealed and labelled storage boxes in a locked room and alarmed room. Access will be denied to all persons with the exception of the Principal Investigator and his designees. Pseudo-anonymised data derived from the study will be kept for 10 years and then archived by Kings College London.

Compliance

The CI will ensure that the trial is conducted in compliance with the principles of the Declaration of Helsinki (1996), and in accordance with all applicable regulatory requirements including but not limited to the Research Governance Framework, Trust and Research Office policies and procedures and any subsequent amendments.

11. Finance and Publication Policy

The intention is for findings from the study to be published in appropriate peer-reviewed scientific journals. Summary findings will be placed on the study website <https://www.kcl.ac.uk/research/mimsa>

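### Both secondary objectives refer to susceptibility, and one to pre-existing oral disease, but infected participants are first sampled and examined after infection, so direction cannot be inferred

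*Protocol*

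**What the plan says.** Objective 1 in Protocol 2.1 is "To determine whether differences in mucosal immunity or differences in the oral microbiome correlate with susceptibility to COVID-19 infection", and also progression and recovery. Objective 2 asks "whether the presence of pre-existing oral disease is related to susceptibility to SARS-CoV2 infection", and also about severity, mucosal immunity and the microbiome. The synopsis likewise refers to susceptibility in both objectives.

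Recruitment is fixed in Sections 3 and 3.1:

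- Asymptomatic/mild: "Asymptomatic/mild subjects will be recruited from those identified as positive for SARS-CoV2 carriage in routine testing at KCL or GSTT".
- Moderate/severe: "Patients will be recruited from those admitted or planned to be admitted to GSTT with a recent onset (≤ 21 days) of symptoms", with a positive PCR.
- Recovered: "Recovered groups: Have had COVID-19 disease proven by PCR testing for SARS-CoV-2". No interval since infection is set.

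Uninfected participants attend once, or return at four weeks (4.4). A subset is sampled after vaccination (Section 3).

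On the oral examination, 4.4 says: "We wish to record the severity and extent of active inflammation of the periodontium". Section 2.2 records the deepest pocket and bleeding for each tooth, and notes missing teeth. The examination is not normally repeated (2.2, 4.5). The case report form in Section 10 has the item "History of previous periodontitis yes /no", with details if yes. Antibiotics and COVID treatment are permitted (3.1).

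**The concern.** Susceptibility and pre-existing are words about time order: the factor has to come before the infection. A comparison of uninfected people with people first measured after infection does not supply that order. The Background section itself says that viral disease alters T cells and cytokines, both systemically and at mucosal surfaces. Antibiotics, acute illness, a hospital stay or disturbed oral hygiene could plausibly also change the flora or gum bleeding.

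A difference between infected and uninfected groups could therefore arise with no link before infection, and be read as an answer to either secondary objective. Other parts of the protocol encourage a directional reading. The figure in Section 1 has oral disease and dysbiosis acting on severity through mucosal immunity, and 5.1 expects to identify therapeutic targets.

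**Working it through.** **Time order.** No figure in the plan bears on this point. Its only sample-size basis, 30 to 50 values per parameter (2.4), comes without alpha, power or effect size, and the argument does not depend on it. The check is to set each group's first measurement against its infection.

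| Sub-group (both populations) | First sample and examination | Measured before infection? |
|---|---|---|
| Asymptomatic/mild | after a positive test, or classified by nucleocapsid antibodies | No |
| Moderate/severe | after a positive PCR, up to 21 days from symptom onset | No |
| Recovered | after past PCR-proven disease, interval open | No |
| Uninfected | single visit, or return at four weeks; post-vaccination subset | Not followed for new infection |

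Three of the four sub-groups have no measurement before infection. Their later samples at about 2, 4 and 12 weeks also start after it. Those samples can inform progression and recovery, but not susceptibility.

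**Which measures are affected.**

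- Immune markers: strongly, because the protocol itself says infection changes them.
- Microbiome: affected, since antibiotics are permitted and sampling follows infection.
- Bleeding or active inflammation: affected, as a state observed on the day. The protocol does not say that COVID changes it.
- Pocket depth: mixed. It can reflect long-standing damage, but it is measured after infection, and 4.4 uses it as a cumulative measure of inflamed area.
- Missing teeth and periodontitis history: weakly affected, because both can predate infection. The history is recalled afterwards.

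**Illustration 1, a yes/no oral measure.** All rates are assumptions. Take no true link, 40% with active inflammation among the uninfected, and a proportion q among the infected because of illness alone. Group size is 100, the maximum in 2.2.

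Odds ratio = [q/(1−q)] / [0.40/0.60]:

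- q = 0.45: 0.818/0.667 = 1.23
- q = 0.50: 1.000/0.667 = 1.50
- q = 0.60: 1.500/0.667 = 2.25

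The chance of p<0.05 in a two-sided two-proportion test with 100 per group is about 11%, 29% and 81%.

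**Illustration 2, a continuous marker.** Again there is no difference before infection, and illness shifts the marker by s standard deviations (assumed). With the normal approximation, the chance of p<0.05 is Φ(s/√(2/n) − 1.96) + Φ(−s/√(2/n) − 1.96). For n = 100 and s = 0.2, s/√(2/n) = 0.2/0.1414 = 1.414, which gives 0.29.

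| Shift s (SD) | 0.1 | 0.2 | 0.3 | 0.4 | 0.5 |
|---|---|---|---|---|---|
| n = 100 per group | 0.11 | 0.29 | 0.56 | 0.81 | 0.94 |
| n = 50 per group | 0.08 | 0.17 | 0.32 | 0.52 | 0.71 |

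Section 2.2 plans immunology on up to 100 per group and microbiome analysis on the first 50. These are single unadjusted tests; the multiplicity corrections in 2.4 would lower the chance for each marker. More participants make such a signal more likely to be significant and do not remove it.

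**The case against.** The objectives use the language of correlation and relation. The data analysis text in 5.5 plans group comparisons to find markers that may indicate pathogenesis, and the figure is offered as a model of possible interrelationships. A reader might infer that the plan would report effects of illness as its causes. The documents do not say that. What they support is that a result could be misread that way, because the two directional words remain in the objectives.

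A reader might also infer that the only oral measure is inflammation after infection. That is not so: missing teeth, pocket depth and periodontitis history are all recorded. Section 5.1 also distinguishes COVID from non-COVID oral disease, although it gives no rule for telling them apart at a single examination.

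The mechanism is uneven too. Acute illness and hospital stay concern mainly inpatients, while some asymptomatic/mild and recovered participants come from routine testing or community sites. The protocol's own statement about viral disease covers T cells and cytokines, not gums or teeth.

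Finally, the choice of exposure variable may be left to a statistical analysis plan, so its absence here is not itself the fault. That does not rescue the word susceptibility: an analysis plan cannot create samples from before infection or change the protocol's objectives.

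**Conclusion.** The point holds as a limit on what the two secondary objectives can claim. For immune markers, the microbiome and bleeding or active inflammation, this design cannot distinguish a factor that preceded infection from a consequence of infection or its treatment. For missing teeth and periodontitis history the concern is weaker.

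The size is unknown. The odds ratios of 1.23 to 2.25 and the chances of 11% to 81% follow from assumed rates, and the second table from assumed shifts. They show how the mechanism works and do not estimate bias in this study. Nor does the point reach the primary comparisons by population and by degree of severity, neither of which is framed as susceptibility.

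**What to change.** 1. In 2.1 and the synopsis, replace *susceptibility to* infection with *association with current or past SARS-CoV2 infection*, and state that direction cannot be inferred. The words *current or past* are needed so that the recovered groups are described correctly.
2. For objective 2, define pre-existing oral disease mainly from history of periodontitis (Section 10) and missing teeth (2.2). Use pocket depth as a supporting marker, because it is measured after infection. Analyse bleeding or active inflammation only as a concurrent finding, in line with the distinction in 5.1 between COVID and non-COVID oral disease.

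This needs an amendment to wording and a choice among items already collected, with no new data. The cost is a more modest claim. The history item is also crude and open to recall bias, which should be acknowledged when results are reported.
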